In work stream 1 we conducted detailed research to define the symptom burden and needs of people with severe memory problems at the end of life, and their family carers. We have undertaken a longitudinal cohort study and have recruited 61 people with severe memory problems (FAST stage 7a and above, doubly incontinent and speaks only 5-6 words per day), 57 residing in care homes and four in their own homes. We have also recruited 26 of their family carers. Results from these studies showed how people with severe memory problems have multiple unmet needs, particularly with regards to management of pain and agitation. They are at high risk of pressure sores and have problems with eating and swallowing. There is lack of individual care planning and consideration of end of life care needs.

Work stream 2

Workshops with health and social care professionals

In work stream 2 in a first cycle of workshops we included a wide range of stakeholders and participants at all levels of responsibility. We conducted two workshops in London and one in each of Edinburgh, Solihull and Belfast. We used clinical vignettes describing people with severe memory problems and asked participants to consider how their care could be enhanced to provide solutions to the issues described.

In a second round of workshops we enhanced the content and face validity of our intervention, by using the RAND/UCLA approach (18). A key aspect of this approach is the Rand Appropriateness Method (RAM) which was used as a way to agree the key components of the intervention. To ensure that we took proper account of context further workshops were held across the four countries of the UK (sites in London, Edinburgh, Solihull, Belfast and Penarth). Before each workshop an online process managed by Survey Monkey, asked stakeholders to rank, for appropriateness, statements describing possible intervention components that were derived from the first round of workshops. Results were then analysed before each workshop and any points of disagreement were discussed further in the

workshop. Following this, participants were asked to rank statements describing components for necessity but independent of economic considerations. Data from all the workshops were pooled and a final bank of statements describing potential components of the enhanced model of care derived.

Interactive qualitative interviews with family carers and healthcare professionals

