 - a. Enhanced care team
 - b. Care home environment and management
 - c. Care home staff
 - d. Family carers
 - e. Residents with severe memory problems

5. Attempt to describe in detail the costs of delivering the intervention at our pilot sites and the costs of each of its sub-components to inform the commissioning process. These costs can be set against potential benefits and recommendations made

RECRUITMENT AND CONSENT PROCEDURES

Location

Through our previous cohort study we have worked with care homes in the Camden and Barnet Commissioning Group areas. We have chosen these as sites for our pilot intervention because we have previous experience of working with local clinicians including GPs and palliative care teams and they represent different location in terms of the socioeconomic and demographic composition of the area.

Recruitment of care homes

After gaining ethical consent for the study we will approach each care home manager by sending them a letter with brief study details. If the manager is interested, senior study staff will then visit the care home and provide further information regarding the project. We will, at the same time, also approach the proprietor or owner of the care home with similar information and seek their written consent for the home to participate in the enhanced care service and the collection of data from the home for the project outcomes.

Consent for implementing the enhanced model of care within the care home

We will be implementing our intervention of the enhanced care model at the level of the care home; our study can therefore be defined as a cluster pilot evaluation. The model of individual informed consent (or nominee assent) to receive the intervention may not be appropriate for a number of reasons. Firstly we are working with existing clinical services to offer an enhancement of usual care which is in line with the recent English Government Dementia and End of life care strategies. Secondly, we will be training and supporting the existing team to enhance and optimise practice, and thus may influence the care of all residents of the home.

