We have consulted the UK Medical Research Council Guidance Document “Cluster randomised trials: methodological and ethical considerations.” Using this framework our intervention is designated as “type A”- interventions that are received (or not) by a whole cluster together so that there is only one decision to be made for the care home. Therefore we use the appropriate Cluster Representation Mechanism (CRM), in our case, the nursing home owners who will give their consent for the intervention to be implemented in their care home. We will also obtain the permission of an ethics committee to implement the enhanced model of care so that the project undergoes appropriate ethical scrutiny. Some evaluation data will be collected at the individual level from the care home and these data will be anonymised, and therefore managers will not be providing any individually identifiable participant data.

Where we will be collecting individual level data, i.e. the qualitative evaluation, resident quality of life and measures from nursing home staff and family carers, we will obtain individual informed consent to participate. We will document how many participants who are approached do consent to us collecting individual level data as this may inform the planning of our future work.

Informing participants about the study

After gaining ethical consent to implement the enhanced care model the research team will meet with care home staff to inform them of the study and to answer or discuss their queries or concerns regarding the study.

Recruitment of people with severe memory problems for evaluation of outcomes

To collect evaluation data we will aim to recruit as many eligible residents as possible from each participating care home. Our criteria have been developed from an existing NHS and Social Care enhanced model of care from South London which has been used by the King’s Fund as an example of UK best practice:

Resident Inclusion criteria

1. Aged over 65 years.
2. Severe memory problems indicating a clinical diagnosis of DSM-IV criteria for dementia (22).
3. Moderately severe or severe memory problems as classified on the Functional Assessment Staging Scale (FAST) grade 6a and above (5) see Table 2.

Plus at least one of the following criteria:

- There are recurrent infections, significant weight loss and poor nutrition level, recurrent fevers, pains, falls, severe pressure ulcers that are not easily amenable to treatment, severe physical frailty.

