Data will be collected at the start of the intervention, and at monthly time points until a resident dies or until the end of the intervention period (6 months). This will ensure a detailed understanding and, because of the mortality rates expected, minimize attrition. Data will be entered into a password protected anonymised database by the research team.

Quantitative analysis

We will use simple descriptive statistics to summarise process data and the outcomes collected by the ICL at the care home level (i.e. number of deaths in the last month etc.) We will describe the demographic and clinical characteristics of residents and family carers who participate in the data collection, as well as symptoms experienced, interventions received and any sentinel events. We will describe the symptom burden and quality of care received using SWEOLCD, QUALID. We will compare the scores to the results of our previous study in order to gain inferences on whether the enhanced care project makes a difference. The results will be summarised using mean and standard deviation or alternatives in case of non-normally distributed data. Appropriate plots will also be produced.

Qualitative analysis

The interviews will be audio-taped, transcribed verbatim and entered onto a qualitative software programme (Atlas-ti) for the coding, management and retrieval of data. Transcripts will be analysed and coded using Thematic Analysis. The data analysis process will follow the guidelines provided by Braun and Clarke (45) to develop meaningful themes and a rigorous approach to data analysis will be adopted by working to the quality framework recommended by Spencer (46). Throughout the analytic process, the researchers will engage in ongoing reflection with the use of memoing and reflective diaries to engage with the data further and refine emergent themes. Data triangulation will be achieved by interviewing both family carers and care home staff from a variety of work roles (i.e., care home manager, health care assistant, nurse) to explore the facilitators and barriers to the implementation of the enhanced model of care from different perspectives.

Final analyses

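### The comparison meant to show whether the intervention makes a difference sets FAST 6a-and-above pilot residents against what is most likely a FAST 7a-and-above cohort, so case mix could be read as an effect or could hide one

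*Protocol*

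**What the plan says.** Three parts of the protocol bear on this.

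- **The comparison.** Data analysis, Quantitative analysis, names the scores: "We will describe the symptom burden and quality of care received using SWEOLCD, QUALID". The next sentence says the team plans to "compare the scores to the results of our previous study in order to gain inferences on whether the enhanced care project makes a difference". It does not name the earlier study. No restriction by dementia stage is attached to the comparison, and no caution about case mix.
- **The likely comparator.** Under Work stream 1 the team reports that it has "recruited 61 people with severe memory problems (FAST stage 7a and above, doubly incontinent and speaks only 5-6 words per day"), of whom "57 residing in care homes and four in their own homes". The Location section ties that study to the pilot areas: "Through our previous cohort study we have worked with care homes in the Camden and Barnet Commissioning Group areas".
- **The pilot population.** The Resident Inclusion criteria require memory problems "classified on the Functional Assessment Staging Scale (FAST) grade 6a and above (5"), and then "Plus at least one of the following criteria". The list covers physical complications, severe persistent distress that is hard to treat, and co-existing disease that makes intrusive treatment less appropriate.

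The Aims describe two care homes, both receiving the intervention. FAST, BANS and the Charlson index are collected at entry (Table 4).

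**The concern.** The comparison is given a causal purpose, and it serves objective 4, which asks whether the model has an impact. With no concurrent control, the earlier study stands in for the untreated group. That works only if the two groups would have had similar scores without the intervention, and their entry rules give reason to doubt it. They differ in the minimum dementia stage, in the extra clinical criterion, and slightly in setting.

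If stage or clinical complexity affects QUALID or carer satisfaction, a difference in scores may reflect who was enrolled and not what was done for them. Equally, a real improvement could be cancelled out. The pilot is meant to inform a definitive trial, so either misreading could carry forward.

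**Working it through.** The protocol states no effect size, SD, alpha or power, and it declines a formal power calculation, so there is no figure to reproduce. The check sets the entry rules side by side and then gauges the scale.

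**1. Entry rules**

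| | Work stream 1 cohort | Pilot |
|---|---|---|
| Minimum FAST | 7a | 6a |
| Continence and speech | Doubly incontinent, 5-6 words a day | Not required |
| Extra clinical criterion | None reported | At least one required |
| Setting | 57 care home + 4 own home = 61 | Care home only |
| Number of residents | 61 | 30 planned, two homes |

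Table 2 of the protocol lists 6a, 6b, 6c, 6d and 6e below 7a. Five sub-stages are thus eligible for the pilot and fell below the cohort's threshold. Urinary incontinence first appears at 6d and faecal incontinence at 6e, so a pilot resident at 6a to 6c need not be incontinent at all.

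**2. Direction**

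The lower FAST threshold makes the pilot group less advanced. The extra criterion makes it sicker or more distressed at a given stage. These may pull in opposite directions, and the protocol gives nothing from which to sign the net bias.

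**3. Scale of the stage component (illustration)**

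Let f be the share of pilot residents at FAST 6a-6e and d the stage 6 versus stage 7 gap in SD units. With no true effect, the shift due to stage is f × d. Neither f nor d is in the document. Taking f = 0.3-0.7 and d = 0.3-0.8:

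- low: 0.3 × 0.3 = 0.09 SD
- middle: 0.5 × 0.5 = 0.25 SD
- high: 0.7 × 0.8 = 0.56 SD

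**4. Random error**

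The 95% half-width in SD units is 1.96 × √(1/n₁ + 1/n₂), ignoring clustering by home:

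- 30 v 61: 1.96 × √(0.0333 + 0.0164) = 0.44
- 30 v 57: 1.96 × √(0.0333 + 0.0175) = 0.44

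Dropping the four cohort members who lived at home costs almost nothing. The upper end of the stage shift exceeds the half-width; the lower end is small beside it.

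**5. After restricting the pilot side to FAST 7a and above**

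The same range of f leaves 30-70% of 30, that is 9-21 residents:

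- 21 v 57: 1.96 × √(0.0476 + 0.0175) = 0.50
- 9 v 57: 1.96 × √(0.1111 + 0.0175) = 0.70

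Restriction removes the stage 6 term. It does not remove the extra criterion, or any difference in the spread of sub-stages within stage 7.

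**The case against.** The strongest reply is that this is a two-home pilot whose first three objectives are feasibility, acceptability and barriers. The quantitative plan offers means, SDs and plots, with no test, threshold or go/no-go rule tied to the comparison. Pilot residents' clinical characteristics will be described, and Final analyses already plans descriptive change over time. Adjustment could properly sit in an SAP. All of that stands, and it limits the consequences. It does not rescue the stated purpose: the protocol itself sets both the pilot's entry rule and the inference to be drawn.

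Several stronger readings are tempting but are not supported:

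- **That the comparator is certain.** The Work stream 1 and Location sections point to the cohort. However, the Clinical assessment and bereavement sections attach reference 25 to the team's cohort study, and the reference list shows reference 25 as an exploratory randomised trial. The identification is an inference.
- **That this is the only statement about effect.** Health economics also asks whether carers gain utility, with no comparator named, and Final analyses describes change over time. It is the only comparison with an outside group.
- **That the protocol commits to unadjusted scores.** It does not say so. The fault is the inferential wording against a differently selected group, not the absence of a covariate model.
- **That the bias favours the intervention.** Its direction is unknown.

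**Conclusion.** The point holds. The protocol proposes to infer an effect from a comparison in which the groups very probably differ by design in dementia stage and clinical selection, and it attaches no safeguard to that inference. A case-mix difference could be mistaken for an effect or could conceal one.

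The mismatch in entry rules rests on the protocol's own text, given that the work stream 1 cohort is the comparator. The size does not. The 0.09-0.56 SD range depends on an assumed stage 6 share and an assumed stage gap, covers stage only, and could be offset or enlarged by the extra criterion. It shows that the problem need not be trivial beside a half-width of 0.44 SD. It does not estimate the actual bias.

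**What to change.** 1. Name the comparator study in Quantitative analysis.
2. Compare pilot residents at FAST 7a or above at entry with the 57 care-home members of the cohort, and show FAST 6 residents separately.
3. Tabulate entry characteristics for both groups side by side: FAST, plus BANS and Charlson where the cohort has them.
4. Flag anyone who took part in both studies. The shared areas make this possible, though the protocol does not say that it happens.
5. Give the difference with a 95% CI.
6. Replace the stated purpose with wording such as: the comparison with the earlier study provides descriptive context and is not evidence of the intervention's effect. Rely mainly on the within-resident change over time already planned in Final analyses.

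Regression adjustment for several covariates is not recommended. With perhaps 9-21 residents from two homes it asks too much of the data, and it needs resident-level cohort records that the protocol does not confirm are available.

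**Cost.** This changes analysis wording and needs no new pilot data, because FAST, BANS and Charlson are already collected at entry. It does need cohort results for the 57 care-home residents. The price is precision: the half-width goes from 0.44 SD to about 0.50-0.70 SD if 30-70% of the 30 residents are at 7a or above (an assumption), and wider still once clustering by home is allowed for.

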The Quality of Life in Late Stage Dementia Scale (QUALID): is a validated scale that assesses quality of life over the prior week (37). (See Appendix 9).

Resource Utilisation in Dementia (RUD)-lite: Resource Utilisation in Dementia (RUD)-lite: Is a short version of the RUD structured interview to assess costs of care including patient accommodation, informal care, community care and hospitalizations (38). (See Appendix 10).

Monthly follow up assessments

Participating residents will be reviewed every four weeks in the care home by the research team, for a maximum of six months, or until death. We will repeat measures: the generalist clinical assessment; Waterlow, Sterling, CMAI, NPI, BANS, PAINAD, SM-EOLD, QUALID, and the RUD-lite. We shall also record prospectively the number of acute hospital admissions, the reasons for these, “burdensome interventions” e.g. enteral feeding tubes (27) and “sentinel events”, defined as “new medical conditions that have the potential to lead to a significant change in health status and a shift in the goals of care” e.g. pneumonia, hip fracture (6). Prescription medications and use will also be collected.

Data collection post death

The Comfort Assessment in Dying with Dementia Scale (CAD-EOLD) (36) (See Appendix 11) will be completed with care home staff within 14 days of the resident’s death to assess their level of comfort and pain in the seven days prior to their death. Through a review of care home notes we shall record use of medication at the end of life (i.e. “just in case” prescribing, opiates, syringe drivers and artificial hydration or nutrition), sentinel events and burdensome interventions. We will examine adherence to any individual care plans which were made.

Outcomes for family carers

Data will be collected independently by the research team during face to face interviews at study entry within 14 days of the initial resident assessment and then every month, by post or over the telephone (family carers’ preference). If family carers are un-contactable for more than 2 months or withdraw from the study we will document the reason and aim to continue to include the person with severe memory problems in the study, unless the carer specifically withdraws their assent.

At project start

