After full data collection ends, we will undertake definitive analyses to detail the demographic features of the cohort and assess the symptom management and their health care needs (using Stirling, Waterlow, NPI and sentinel events), taking into account repeated measures on individual subjects. We shall describe the level and nature of unmet needs and examine descriptively (using mean and standard deviations or suitable alternatives in case of non-normally distributed data and graphs) how comfort and quality of life change over time (using PAINAD, SM-EOLD, SW-EOLD and QUALID). We will describe the trajectory of carer wellbeing (HADS and Zarit Buden Interview) during their friend/relative's final stages of life with severe memory problems and how this may change if the resident dies, using plots of the of wellbeing over time.

Sample size

This is a pilot study and as such a formal power calculation is not appropriate. Numbers are chosen on pragmatic grounds as sufficient to demonstrate feasibility in terms of recruitment and acceptance of the intervention. We will aim to recruit 30 residents with severe memory problems from two care homes from which to collect individual outcome data.

Health economics

Health economic evaluation will consider resource allocation in caring for patients with severe problems and, where relevant, in their last 6 months of life, as well as the quality of life of their family carers and associated economic impact on these family carers in this period.

Data on resource and service use for people with severe memory problems (RUD-Lite) and economic burden on family carers (Zarit Burden Interview) will be collected both at baseline and monthly after the enhanced care project has been implemented. These data will be collated with unit costs data from *Unit Costs of Health and Social Care (2012)* (47;48) to obtain costs per patient from NHS (such as averted hospital admission, costs for a typical episode), costs from personal social services (such as training and education for care home staff) and costs from societal perspectives (such as local commissioners' decisions on scarce resource allocation, additional costs to public purse where caring responsibilities had been met by the state instead of family carers).

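### Means of PAINAD, SM-EOLD and QUALID over time would cover a changing set of living residents and may be distorted by deaths, and monthly visits cannot reduce loss through death

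*Protocol*

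**What the plan says.** The DATA ANALYSIS section of the protocol sets collection at the start and then "at monthly time points until a resident dies or until the end of the intervention period (6 months". Monthly follow up assessments says the same of the resident visits, which run every four weeks "for a maximum of six months, or until death". Table 4 shows PAINAD, SM-EOLD and QUALID at the start and during the project, and none of them after death.

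Final analyses then describes "how comfort and quality of life change over time (using PAINAD, SM-EOLD, SW-EOLD and QUALID", to be done descriptively, "using mean and standard deviations or suitable alternatives in case of non-normally distributed data and graphs". It gives no rule for how deaths enter this summary. Allowance for repeated measures is stated one sentence earlier, for Stirling, Waterlow, NPI and sentinel events. The following sentence, on carers, does plan for the resident's death.

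On loss to follow-up, DATA ANALYSIS says of the monthly schedule: "This will ensure a detailed understanding and, because of the mortality rates expected, minimize attrition". No mortality rate is given.

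Two instruments are used after death. CAD-EOLD covers the last seven days of life (Data collection post death; Data collection in bereavement) but is not named in the analysis sections. The satisfaction scale SW-EOLD is completed by carers monthly and again in bereavement.

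**The concern.** If the residents who die tend to have the worse scores, the mean at a late visit describes a fitter group than the mean at baseline. The line on the graph can then move although no resident has changed, or stay flat while residents decline.

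Death is not a remote possibility here. The protocol itself refers to expected mortality. Entry requires FAST 6a or above plus a further marker such as recurrent infections, weight loss, severe frailty or persistent distress. A link between poor comfort or quality of life and death is plausible in such residents, though the protocol does not document one.

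At stake is how the resident results are read. Objective 4 asks about impact, including on residents, and the study has no concurrent control. The one remark on attrition offers visit frequency as the answer, which does not address the changing denominator.

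**Working it through.** The protocol has no power, event or mortality figure to reproduce. It states "This is a pilot study and as such a formal power calculation is not appropriate" and, on size, "We will aim to recruit 30 residents with severe memory problems from two care homes". What follows is an illustration.

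**Inputs.** From the protocol: 30 residents, monthly visits, six months, scoring stops at death. Assumed: six-month mortality m of 20%, 30% or 40%; a death hazard ratio HR of 1.25, 1.5 or 2.0 per SD of worse score; a stable standard-normal score x for each resident (positive = worse), with no change in anyone.

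**Step 1: residents left at month 6.** 30 × (1 − m) = 24, 21 and 18. With unit SD, the standard error of their mean is 1/√24 = 0.20, 1/√21 = 0.22 and 1/√18 = 0.24 SD.

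**Step 2: mean score among those left.** Survival to month 6 is S(x) = exp(−h·HR^x), with h solved so that average survival equals 1 − m. The survivor mean is E[x·S(x)] / E[S(x)]. By numerical integration, in SD units (negative = apparent improvement):

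| Six-month mortality | HR 0.8 | HR 1.0 | HR 1.25 | HR 1.5 | HR 2.0 |
|---|---|---|---|---|---|
| 20% | +0.05 | 0 | −0.05 | −0.09 | −0.15 |
| 30% | +0.08 | 0 | −0.08 | −0.14 | −0.23 |
| 40% | +0.11 | 0 | −0.11 | −0.20 | −0.31 |

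The baseline mean of all residents is 0, and the change of each resident from their own baseline is 0 by construction. Every non-zero entry therefore comes only from who is left. The columns at 0.8 and 1.0 show that the sign depends on the assumed link.

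**Step 3: masking of real decline.** Let every resident worsen by 0.05 SD a month, so 6 × 0.05 = +0.30 SD. With HR 2.0 the survivor mean shows 0.30 − 0.23 = +0.07 at 30% mortality and 0.30 − 0.31 = −0.01 at 40%.

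**Step 4: what monthly visits achieve.** Assume a constant hazard. The share alive at the first follow-up visit is (1 − m)^(1/6), which is 96% at 20% mortality and 92% at 40%. The mean number of visits completed, Σ(1 − m)^(k/6) for k = 1 to 6, is 5.3 and 4.5 of 6. A single visit at month 6 would reach 80% and 60%. Monthly visits thus recover many scores before death, but the share alive at month 6 is the same under either schedule.

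**The case against.** Much of the case on the other side stands.

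- **The method is inferred.** A reader might infer that the protocol fixes visit-by-visit means over survivors. It does not say so. Graphs and alternatives could include individual profiles, and an analysis plan not shown here may settle the detail. What the protocol does fix is that three scales stop at death and that means and SDs are the default summary.
- **The direction is not established.** A reader might infer that scores will drift towards better. The documents give neither a mortality rate nor a link between these scores and death.
- **The trajectory is not the main evidence of impact.** With no concurrent control, a reader might infer that it is. Quantitative analysis instead draws the inference from a comparison with the previous study, and the course over time is only described. QUALID is, however, one of the scales named just before that comparison.
- **Not every listed scale is affected alike.** SW-EOLD is rated by carers and also collected in bereavement. CAD-EOLD does capture comfort near death, though no analysis names it.
- **The shift is small beside sampling error.** The central 0.14 SD is below the standard error of 0.22 SD. That limits what could be concluded from any month-6 mean, but it does not remove a shift that is systematic.
- **The attrition remark has a sound core.** Frequent visits do save data before death, so the sentence needs rewording, not deletion.

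**Conclusion.** The point holds as a matter of interpretation in a descriptive pilot. No test or sample-size figure is affected. Means of PAINAD, SM-EOLD and QUALID over time would combine change within residents with change in who remains, and the protocol's only stated answer does not deal with this.

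Under the assumed 20-40% mortality and HR 1.25-2.0, the month-6 mean moves by about 0.05-0.3 SD with no true change. Towards better is the plausible direction, given the entry criteria, but it is an assumption. A modest real decline could be partly or wholly hidden. Correcting this is a worthwhile, inexpensive improvement.

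**What to change.** In Final analyses:

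- Summarise PAINAD, SM-EOLD and QUALID as change from each resident's own baseline.
- Show the number alive and the number assessed at each month beside every summary.
- Display residents who died and residents who survived separately, or align those who died to time before death, with CAD-EOLD alongside. This is needed as well as the paired change, because paired change at month 6 still describes only those who reached it.
- State that the month-6 mean is not to be read against the full-sample baseline mean.
- Treat SW-EOLD separately, marking which ratings were made in bereavement.

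In the opening paragraph of DATA ANALYSIS, replace the claim "because of the mortality rates expected, minimize attrition" with a statement that monthly visits reduce the data lost before death but do not reduce loss through death.

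The cost is a little more analysis, some extra table columns and plots, and smaller displayed subgroups. No new data are required.
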